**Laboratory Pain Assessment:**

Participants will undergo quantitative sensory testing to measure pain threshold. Ten randomly ordered warming (5) and cooling (5) sequences will be administered with variable (2-10 sec random) lead times and a warm/cool rate of 0.2° C per sec until the subject indicates that a temperature change was perceived. **THERMAL PAIN THRESHOLD ASSESSMENT:** Cutaneous heat and cold stimuli will be delivered via a Contact Heat-Evoked Potential Stimulator (CHEPS; Medoc, USA) attached to the volar forearm of each subjects left arm. The Method of Limits will be used. The thermode will heat/cool at a rate of 0.5° C per second until the subject indicates that pain was perceived. The procedure will be repeated 10 times (5 hot and 5 cold) and mean values will be used. **THERMAL PAIN MAGNITUDE ESTIMATION:** Twelve separate 2-second thermal stimuli (4 stimuli each at 46°, 47.5°, 49° C; randomized) will be applied to each subject's left volar forearm. The target temperature will be sustained for 2 seconds and the thermode will immediately cool to 32° C. After termination of each stimulus, subjects will rate both the intensity and the unpleasantness of the stimulus using the computerized VAS. **THERMAL WIND-UP PAIN ESTIMATION:** The CHEPS will be used to deliver 20 very brief noxious thermal stimuli to the left volar forearm of subjects at the rate of 1 stimulus (0.75 sec duration) every 1.5 seconds (at 49°C) thus facilitating C-fiber activation and receptive field expansion of the WDR neurons in the dorsal horn. Subjects will continuously indicate level of pain intensity using a dynamic computerized VAS. **MECHANICAL PAIN THRESHOLD ASSESSMENT:** The IITC Life Sciences Digital Anesthesiometer will be used to apply pressure to the dorsal surface of the distal phalange of the digit minimi of the left hand. Pressure will be increased at the rate of 10 grams per second. Participants will stop the stimulus when pressure reaches the pain threshold and the pressure will be recorded in grams.

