**STUDY DESIGN AND PROCEDURES:**

Interested participants will call and be pre-screened on the telephone. If interested participants meet the inclusion criteria they will be scheduled for one appointment (lasting approximately 1 hour). Upon coming to the Brain Stimulation Laboratory for the appointment, participants will review and sign the informed consent document. Written informed-consent will be obtained by one of the study investigators or the study coordinator. Participants will complete the Center for Epidemiological Studies 10-item depression scale (CESD), the Beck Anxiety Inventory (BAI), the Reiss-Epstein-Gursky A.S.I., and the Brief Pain Inventory (BPI).

After completing the initial questionnaires they will be taken to the laboratory where they will undergo five trials of the heat tolerance laboratory pain test. The tDCS electrodes will then be placed and fastened with Velcro straps, and the tDCS session will be started. During the tDCS stimulation, participants will undergo the cognitive or educational component of the study as well as pain tolerance assessment procedures every 5 minutes. Patients will randomly receive one of four cognitive behavioral therapy interventions administered through headphones so that the research staff can remain blind. The four cognitive behavioral therapies include Pain-Catastrophizing Cognitive Intervention, Cognitive-Behavioral Distraction Intervention, Cognitively-Mediated Relaxation Intervention, Education-Only Control Condition.

After completion of the tDCS session, participants will again undergo five consecutive trials of the quantitative sensory testing.

At the completion of each appointment participants will be assessed for adverse effects of the stimulation, and they will be asked if they think they received real or fake stimulation and will rate how confident they are in their answer using a 0-10 scale (0= guessing 10= absolutely sure). Participants will also be asked to complete a short supplemental form at the end of the appointment. Participants will also be compensated \$40 in cash at that time for their participation in the study.

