**ANALYSIS:**

3 variable MANCOVA will be used to investigate whether change scores (from pre- to post-stimulation) in pain tolerance ratings (i.e., the temperature that participants were no longer able to tolerate the heat stimulus) are significantly affected by stimulation condition. Anodal, Cathodal, and Sham stimulation will be randomly paired with one of the four cognitive behavioral therapies. Both the stimulation and cognitive behavioral therapy will be run through a randomized computer system so as to maintain blinding. A 4X3X2 [CBT group BY tDCS group BY time (pre-post)] mixed multiple analysis of covariance (MANCOVA) will be conducted with the multiple QST values as dependent measures and while controlling for physiological indices across phases (pre- and post-intervention. Gender, age, and race will be controlled in all analyses, although specific demographic variable differences are not expected for the present study. Scores on initial tests (i.e., CESD, BAI, and BPI) may also be examined as control variables

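### The pain test is named differently before and after stimulation, and the only model that names CBT group does not name tolerance, the outcome of both aims

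*Combined protocol and SAP*

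**What the plan says.** All references are to the combined protocol and SAP.

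- **Study Design and Procedures, before stimulation:** "they will undergo five trials of the heat tolerance laboratory pain test".
- **Same section, during stimulation:** "pain tolerance assessment procedures every 5 minutes".
- **Same section, after stimulation:** "participants will again undergo five consecutive trials of the quantitative sensory testing".
- **Laboratory Pain Assessment:** "Participants will undergo quantitative sensory testing to measure pain threshold". Five components follow: temperature detection, thermal pain threshold, magnitude estimation, wind-up and mechanical threshold. The thermal threshold ramp runs "until the subject indicates that pain was perceived".
- **Analysis, first description:** "3 variable MANCOVA will be used to investigate whether change scores" in tolerance differ by stimulation arm. Tolerance is defined here and nowhere else, as "the temperature that participants were no longer able to tolerate the heat stimulus".
- **Analysis, second description:** a 4×3×2 mixed MANCOVA (CBT group, tDCS group, pre-post time). Its dependent measures are several QST values, and physiological indices are a covariate.
- **Specific Aims:** both aims, including whether a cognitive intervention adds to tDCS, are stated in terms of pain tolerance.

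**The concern.** Tolerance and QST are not synonyms in this protocol. A threshold ramp stops when pain begins; tolerance is where the participant can bear no more. A team that follows Study Design and Procedures to the letter would run one kind of test before stimulation and another after it. In a single-visit study, a baseline not taken cannot be recovered.

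The second issue is which model answers the combination question. The sentence on tolerance names only stimulation as the effect. The model that contains CBT group has QST values as outcomes. As written, no model explicitly tests the second aim on the outcome in which that aim is stated.

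**Working it through.** The plan gives no figure to reproduce here, so the check is mainly a comparison of sections.

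**1. What each reading of the post-stimulation sentence supplies**

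| Reading | Tolerance, pre / post | QST battery, pre / post | Consequence for Analysis |
|---|---|---|---|
| Literal | named / not named | not named / named | Tolerance change has no post value; the QST time factor has no pre value |
| Same tolerance test twice | named / named | not scheduled before and after | Tolerance change can be computed; the 4×3×2 MANCOVA lacks its stated outcomes |
| Tolerance and battery at both times | both | both | Both analyses can be run, but the section does not say this |

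**2. Which reading is likelier.** The word *again* and the matching count of five favour the second row. So do the battery's own counts: detection 5 + 5 = 10, thermal pain threshold 5 + 5 = 10, magnitude 4 × 3 = 12, wind-up 20, mechanical not stated. Five trials of the battery fits none of them. The nearest match is the five hot threshold ramps ("The procedure will be repeated 10 times (5 hot and 5 cold"), but those stop at pain, not at tolerance.

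**3. In-session values.** Tolerance is also assessed during stimulation, but Analysis uses only pre and post, so these values do not fill the gap.

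**4. Outcome against factor.** The tolerance sentence names stimulation and not CBT group; the 4×3×2 model names CBT group and not tolerance. The phrase *3 variable* may mean CBT, tDCS and time, which would make Analysis one model described twice. The text does not say so, and the two descriptions would still name different outcomes. The difference in form (change score or time factor) matters less: with two time points and no time-varying covariate, the group-by-time test is the change-score comparison.

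**5. Covariate.** Physiological indices are not listed as collected under Laboratory Pain Assessment, Study Design and Procedures, or Sources of Materials. The last list is weak evidence alone, since it also omits the A.S.I., which is administered.

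**6. Precision, only if a baseline were actually missed.** Assume equal pre and post variance σ² and pre-post correlation r between 0.5 and 0.8; neither is in the documents. Variances per participant:

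- post value only: σ²
- change score, as planned: 2(1 − r)σ²
- post value adjusted for pre: (1 − r²)σ²

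Against the planned change score, 360 post-only participants equal 360 × 2(1 − r):

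- r = 0.5: 360 × 1.0 = 360, no loss
- r = 0.8: 360 × 0.4 = 144

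The adjusted analysis relative to the change score is (1 − r²) / [2(1 − r)] = (1 + r)/2, which is 0.75 at r = 0.5 and 0.90 at r = 0.8. It never exceeds 1, so adjustment is at least as precise.

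**The case against.** The strongest reply is that QST is a loose label and the same tolerance test was always meant at both times. That is the likelier reading, and it rescues the tolerance change score. It does not rescue the MANCOVA, whose several QST values then have no clear pre and post schedule.

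A second reply is that the battery's intent is visible: Laboratory Pain Assessment says participants will undergo it, the same term is used after stimulation, and Analysis gives QST values a pre-post factor. This stands as evidence of intent. It would be too strong to say the battery was never planned; what is missing is a clear schedule for it on both sides of stimulation.

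Two stronger readings are tempting:

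- **Tolerance will not be measured after stimulation, so its baseline is wasted.** This rests on the literal reading, which the wording makes less likely. Any precision loss is conditional on it and can be nil against the planned change score.
- **The outcome for the combination question is free to be picked after the data are seen.** Specific Aims fixes tolerance as the outcome of both aims, and Analysis defines it as a temperature. What remains is that the CBT-by-tDCS test on tolerance is not stated explicitly.

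**Conclusion.** The concern holds as an inconsistency between three sections, and it should be fixed. Followed literally, each of the two outcomes in Analysis lacks one of its two time points. On the likelier reading, the tolerance analysis is feasible but the 4×3×2 MANCOVA lacks its stated outcomes. On either reading, tolerance has no described procedure, and no model explicitly tests the combination aim on it.

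The documents do not show that a measurement will be missed, so no number of lost participants can be attached to the point. The conditional range of 360 down to 144 applies only if a pre value is in fact not taken, and it rests on the assumed r and equal variances. Confidence is high for the mismatch itself, not for any resulting harm.

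**What to change.** Reconcile the three sections:

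1. **Study Design and Procedures:** name the same five-trial heat-tolerance test before and after stimulation. *Cost: wording.*
2. **Laboratory Pain Assessment:** describe that test, keeping its stopping instruction distinct from the pain-threshold stop. *Cost: wording.*
3. **Analysis, tolerance:** name tolerance as the outcome of both the tDCS and the CBT-by-tDCS tests, analysed as the mean of the post trials adjusted for the mean of the pre trials. *Cost: a small change of analysis from the change score, using the same two sets of trials.* Naming the outcome is what the inconsistency requires; the adjustment is recommended for precision.
4. **Analysis, MANCOVA:** limit the pre-post model to measures scheduled at both times. The sponsor either schedules the battery before and after stimulation or takes it out of this model. *Cost: scheduling it adds time to a visit of approximately 1 hour, by an amount the documents do not let one calculate; removing it is wording.*
5. **Covariate:** remove physiological indices unless they are defined and their measurement scheduled. *Cost: removal is wording; keeping them means adding a measurement.*

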**ANALYSIS:**

3 variable MANCOVA will be used to investigate whether change scores (from pre- to post-stimulation) in pain tolerance ratings (i.e., the temperature that participants were no longer able to tolerate the heat stimulus) are significantly affected by stimulation condition. Anodal, Cathodal, and Sham stimulation will be randomly paired with one of the four cognitive behavioral therapies. Both the stimulation and cognitive behavioral therapy will be run through a randomized computer system so as to maintain blinding. A 4X3X2 [CBT group BY tDCS group BY time (pre-post)] mixed multiple analysis of covariance (MANCOVA) will be conducted with the multiple QST values as dependent measures and while controlling for physiological indices across phases (pre- and post-intervention. Gender, age, and race will be controlled in all analyses, although specific demographic variable differences are not expected for the present study. Scores on initial tests (i.e., CESD, BAI, and BPI) may also be examined as control variables

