**PARTICIPANTS:**

Subjects will be 360 healthy adult volunteers. Subjects will be between the ages of 18 years and 75 years recruited from the greater Charleston area via flyers and newspaper advertisements. Subjects will be paid for their participation.

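### The pain-tolerance change-score analysis leaves out baseline tolerance, which is already measured; adding it as a covariate is a near-free gain in precision of uncertain size

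*Combined protocol and SAP*

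**What the plan says.** The Analysis section describes two models. The first concerns heat tolerance: "3 variable MANCOVA will be used to investigate whether change scores (from pre- to post-stimulation) in pain tolerance ratings" depend on stimulation condition. The second is a mixed MANCOVA of the sensory-testing values with CBT group, tDCS group and time (pre, post) as factors, fitted "while controlling for physiological indices across phases (pre- and post-intervention".

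The covariates are listed: "Gender, age, and race will be controlled in all analyses", and "Scores on initial tests (i.e., CESD, BAI, and BPI) may also be examined as control variables". Baseline tolerance is named in neither list.

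It is nevertheless collected. Under Study Design and Procedures, once the questionnaires are complete and before the electrodes are placed, "they will undergo five trials of the heat tolerance laboratory pain test". After the session, "participants will again undergo five consecutive trials of the quantitative sensory testing". The Participants section sets the size: "Subjects will be 360 healthy adult volunteers". No power calculation, effect size, SD, significance level or allocation ratio is given.

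**The concern.** The pre-treatment value of an outcome is usually its strongest predictor. The plan adjusts for demographics in which it expects no differences, and may adjust for mood and pain questionnaires, but not for the starting value of tolerance itself. Subtracting baseline is not the same as adjusting for it. A change score fixes the slope of post on pre at 1, whereas a covariate lets the data estimate it. If the true slope is not 1, the change score carries avoidable variance.

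What is at stake is precision for the tDCS comparison. Since 360 comes without a power calculation, there is no stated margin to absorb a loss.

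**Working it through.** **Does the plan already adjust for baseline?** No.
- In the second model the pre value is a level of the outcome. With two time points, a group-by-time test is the between-group test of the change score, so the slope stays fixed at 1.
- The physiological indices are not defined. Tolerance is the dependent variable of the first model, and nothing suggests that the phrase means its baseline.

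**Inputs.** From the documents: 360 subjects, three tDCS conditions, four cognitive interventions, and tolerance measured before stimulation. Assumed: equal allocation (120 per tDCS group, 30 per cell), a two-sided 5% level, pre-post correlation ρ from 0.5 to 0.9, and k = post SD / pre SD of 0.8, 1 or 1.2. Both ρ and the SDs are taken after allowing for the other covariates. The plan has no figure of its own to reproduce.

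**Variances**, in units of the squared pre SD:
- change score: 1 + k² − 2ρk
- baseline-adjusted: k²(1 − ρ²)
- difference: (1 − ρk)², which is never negative and is zero only when the slope ρk equals 1

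With k = 1 the ratio reduces to (1 + ρ)/2. Example with k = 1.2 and ρ = 0.5: change 1 + 1.44 − 1.20 = 1.24; adjusted 1.44 × 0.75 = 1.08; ratio 0.871.

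Variance ratio, adjusted to change. In brackets is 360 × ratio, the number of subjects that would give the same precision with baseline adjustment:

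| ρ | k = 0.8 | k = 1 | k = 1.2 |
|---|---|---|---|
| 0.5 | 0.571 (206) | 0.750 (270) | 0.871 (314) |
| 0.7 | 0.628 (226) | 0.850 (306) | 0.966 (348) |
| 0.8 | 0.640 (230) | 0.900 (324) | 0.997 (359) |
| 0.9 | 0.608 (219) | 0.950 (342) | 0.977 (352) |

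At k = 1.2 and ρ = 0.833 the slope is 1 and the ratio is 1.000. A simulation of the 12-cell design with k = 1 (6,000 runs) gave ratios of 0.749, 0.842, 0.912 and 0.960 at the four correlations. Both estimators averaged the true difference of 0.20, as expected without bias.

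**What this means for the tests** (k = 1, effects in pre SDs, change score / adjusted):
- Difference between two tDCS groups detectable with 80% power = (1.96 + 0.84) × √(2 × variance/120).
- Three-group tDCS test with one group differing by 0.2 SD: noncentral F on 2 degrees of freedom, noncentrality 120 × (2/3) × 0.04 / variance = 3.2 / variance.
- Four-cell interaction contrast of 0.5 SD: standard error √(4 × variance/30).

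| ρ | Detectable difference | Power, three-group test | Power, interaction |
|---|---|---|---|
| 0.5 | 0.362 / 0.313 | 34% / 44% | 28% / 35% |
| 0.7 | 0.280 / 0.258 | 53% / 60% | 42% / 48% |
| 0.8 | 0.229 / 0.217 | 71% / 76% | 58% / 62% |
| 0.9 | 0.162 / 0.158 | 95% / 96% | 86% / 88% |

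**Cost.** With 12 cells, residual degrees of freedom are 360 − 12 = 348. Allowing 1 for gender, 1 for age and 4 for race (five categories in the enrolment table) leaves 342; baseline takes this to 341. Estimating the slope inflates the variance by about 1 + 1/340, or 0.3%. In the least favourable case (slope exactly 1, k = 1.2, variance 0.44), power for a 0.2 SD difference between two tDCS groups falls from 64.4% to 64.3%. With equal SDs this cost outweighs the gain only at ρ of about 0.995 or more.

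**The case against.** The strongest reply is that nothing here is wrong. The change score is a valid estimator of the same effect, and the size of any gain cannot be drawn from the documents. Pre and post tests fall within one appointment of about an hour and each uses five trials, so the correlation may well be high. At ρ = 0.9 with equal SDs the detectable difference moves only from 0.162 to 0.158. With k = 1.2 and ρ of 0.7 to 0.9 there is almost no gain. All of this stands, and it is why the whole range should be read rather than the ρ = 0.5 row. It does not argue against the change, because the possible loss is about 0.1 point of power whatever ρ turns out to be.

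A second objection concerns the model. The tolerance sentence mentions stimulation condition only, whereas the figures assume a 12-cell layout and a single outcome. That is fair, but it has little effect on the cost: with three tDCS groups alone the residual would be 360 − 3 − 6 = 351 degrees of freedom. The powers are univariate and do not describe a multivariate test.

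A reader might go on to infer that the MANCOVA of the sensory measures should be split into separate ANCOVAs, each with its own baseline. The documents do not support that. The Laboratory Pain Assessment and Study Design sections do not clearly place the full battery before stimulation, so no gain can be shown there. Splitting would also give up the joint test: eight independent tests at 5%, an illustrative number, carry a 1 − 0.95⁸ = 34% chance of at least one false positive.

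**Conclusion.** The point holds as a free improvement, not as the correction of an error. The tolerance analysis omits a covariate that is already collected. Including it lowers the variance by anything from almost nothing to about 43% over the assumed range (ratios from about 1.00 down to 0.57), and by 5% to 25% if the pre and post SDs are equal. The direction follows from algebra; the size rests entirely on assumed correlations and SDs.

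Two stronger readings should be resisted. One is that the planned analysis is biased: conditions are assigned at random, so it is not. The other is that the adjustment makes the tDCS-by-cognitive-intervention question in the Specific Aims adequately powered. The variance ratio is the same for every contrast, and with cells of about 30 a four-cell contrast of 0.5 SD still has only 35% to 62% power after adjustment at ρ of 0.5 to 0.8. Limited power for that question is mainly a matter of sample size and remains.

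**What to change.** In the Analysis section, prespecify each subject's mean pre-stimulation heat tolerance as a covariate in the tolerance model, alongside gender, age and race. The outcome may be post-stimulation tolerance or change; once baseline is in the model, the treatment estimate is the same. Do not add baseline as a covariate to the model with time as a factor, where it is already an outcome level, and leave the joint analysis of the sensory measures as planned.

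This relies on the post-stimulation trials repeating the baseline heat-tolerance test. The two are named differently under Study Design and Procedures, so the text should confirm it; the change score already requires the same match.

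The cost is one sentence of analysis text, that confirmation, and one of roughly 342 residual degrees of freedom. No new data are needed if the two tests are the same.

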**A. SPECIFIC AIMS**

*List the broad, long-term objectives and the goal of the specific research proposed, e.g., to test a stated hypothesis, create a novel design, solve a specific problem, challenge an existing paradigm or clinical practice, address a critical barrier to progress in the field, or develop new technology.*

**This study aims to evaluate the effectiveness of transcranial direct current stimulation (tDCS) and a brief cognitive intervention in increasing pain tolerance. Specifically, this study will determine whether healthy subjects will indicate greater pain tolerance to a heat stimulus following a single 20-minute session of anodal vs. cathodal tDCS (compared to sham tDCS). This study will also test whether providing one of four cognitive pain-managament interventions (conducted during the tDCS session) will result in even greater pain tolerance among subjects who also received tDCS .**

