**B. BACKGROUND AND SIGNIFICANCE**

*Briefly sketch the background leading to the present application, critically evaluate existing knowledge, and specifically identify the gaps that the project is intended to fill. State concisely the importance and health relevance of the research described in this protocol by relating the specific aims to the broad, long-term objectives. If the aims of the study are achieved, state how scientific knowledge or clinical practice will be advanced.*

**Recently, the use of low amplitude direct current stimulation of the human cortex has received attention as a possible treatment for pain (Been et al, 2007). This technique (called transcranial direct current stimulation or tDCS) involves the placement of two sponge electrodes over separate areas of the scalp. tDCS has been shown to be capable of changing the excitability of the superficial neurons immediately**

beneath the sponge electrodes. Evidence suggests that anodal stimulation is associated with increased cortical excitability and cathodal stimulation is associated with decreased cortical excitability (Been et al., 2007). The electrodes can therefore be placed on the scalp according to the desired part of the cortex with which to excite.

Across experimental and clinical studies, investigators have demonstrated the analgesic effects that tDCS can have in the experience of pain (see Fregni et al., 2007 for a review). The dorsolateral prefrontal cortex (dIPFC) is one area of the brain that may be particularly relevant in using tDCS to reduce perceived pain and increase pain tolerance. For example, in a study of patients who had undergone ERCP surgery (Borckardt et al., 2011a), there was a significant decrease in reported pain scores and in medication use among the patients who received tDCS. The dIPFC appears to affect emotional aspects of the pain experience and one's perceived controllability of pain (Boggio et al., 2008; Borckardt et al., 2011b), and this may be one way that tDCS affects changes in pain perceptions when anode currents are directed at the dIPFC.

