There is also extensive research to support the use of cognitive-behavioral therapy (CBT) in the treatment of pain conditions (e.g., Chen et al., 2004; McCracken & Turk, 2002; Morley et al., 1999). It is well established that CBT is effective in greatly reducing the suffering that patients with chronic pain endure. There are three main elements to CBT for chronic pain, which include education about how emotions and behaviors can affect one's experience of pain, training in coping strategies to better manage the pain experience (including both behavioral and cognitive strategies), and assistance in the maintenance of those coping strategies (Kerns et al., 2011). Providing accurate information about one's pain experience and training individuals to think about their pain experience in a different way is one relevant aspect of pain treatment that may relate to activity of the prefrontal cortex.

Despite all of the evidence promoting the use of CBT in treating pain conditions, many individuals still do not benefit from this kind of intervention (Kerns et al., 2011), and it is possible that the use of tDCS over the dIPFC may enhance the potential benefit of cognitive interventions in treating pain. The goal of this study is to investigate how both tDCS and a brief cognitive intervention affect pain tolerance in an experimental setting, and specifically whether the combination of tDCS and a cognitive intervention will enhance pain tolerance. Ultimately, we hope our results will further support the use of tDCS for therapeutic applications in the area of pain management, as well as provide initial evidence of its benefit in combination with cognitive-based treatments for pain that are already in use.

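### The aims ask for comparisons with sham and for an added benefit of the cognitive intervention, but the analysis section states only omnibus tests, names no contrast, and does not list its QST outcomes

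*Combined protocol and SAP*

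**What the plan says.** Section A (Specific Aims) sets two questions about one outcome, tolerance to a heat stimulus. Aim 1 concerns tolerance "following a single 20-minute session of anodal vs. cathodal tDCS (compared to sham tDCS"), so it has three arms with sham as the stated comparator. Aim 2 asks whether one of four cognitive interventions "will result in even greater pain tolerance among subjects who also received tDCS".

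Section B gives the rationale. Anodal stimulation is linked with raised cortical excitability, while "cathodal stimulation is associated with decreased cortical excitability". The emotional and controllability role of the dorsolateral prefrontal cortex is offered as one way that "tDCS affects changes in pain perceptions when anode currents are directed at the" dlPFC. On the combination, tDCS "may enhance the potential benefit of cognitive interventions in treating pain", and the goal is to learn "specifically whether the combination of tDCS and a cognitive intervention will enhance pain tolerance".

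Section D, Analysis, describes a MANCOVA of whether pre-to-post changes in tolerance "are significantly affected by stimulation condition". It then describes a mixed MANCOVA of CBT group by tDCS group by time that "will be conducted with the multiple QST values as dependent measures". Sham appears there only as a level to which people are randomised. Education-Only is called a control condition under Study Design and Procedures, but Analysis does not mention it. No pairwise comparison, follow-up rule or multiplicity rule is given in either place.

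**The concern.** Aim 1 asks which arm differs from sham, and in which direction. Aim 2 asks whether particular combinations do better than something else. The analysis asks only whether the three stimulation means, or the cells of the 4 x 3 layout, are all alike. Followed as written, it never compares an active arm with sham. The comparisons that answer the aims, and their error control, would be chosen after the data are seen.

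This matters more than usual here, because the background has the two active arms acting on excitability in opposite directions. A three-arm test can then be significant mainly because anodal and cathodal differ from each other. That difference is part of Aim 1, but it does not say whether either arm differs from sham.

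The outcome set is open too. The Laboratory Pain Assessment section describes detection, threshold, magnitude, wind-up and mechanical measures, but no tolerance procedure. The reader cannot tell whether tolerance is among the MANCOVA's dependent variables.

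**Working it through.** **Inputs.** N = 360 (Participants); 3 tDCS levels and 4 CBT levels (Analysis). The documents give no effect size, SD, alpha, power or allocation ratio, so there is no planned figure to reproduce. *Assumptions:* equal allocation (360/3 = 120 per tDCS arm; 360/12 = 30 per cell), two-sided 0.05, no dropout, no gain from covariates, and effects in SD of the tolerance change score.

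**Terms the model contains.** tDCS x time has 3 - 1 = 2 df. CBT x time has 4 - 1 = 3 df. CBT x tDCS x time has 2 x 3 = 6 df. The last is the only stated test that bears on the combination, and the text does not name it as the test of Aim 2.

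**Aim 1, omnibus test.** Noncentrality = n x sum of squared deviations of the arm means from their average; F on 2 and 357 df, critical value 3.02.
- Anodal +0.2, cathodal -0.2, sham 0: 120 x (0.04 + 0.04 + 0) = 9.6, power **0.795**.
- Cathodal -0.4, others 0: the average is -0.133, so 120 x (0.0178 + 0.0178 + 0.0711) = 12.8, power **0.901**, with anodal equal to sham.

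**Aim 1, contrast with sham.** Noncentrality = d / sqrt(2/120); critical t 1.967.
- d = 0.2: 0.2/0.1291 = 1.549, power **0.339** for each active arm.
- Joint behaviour in the +0.2/-0.2 case (simulation, 400,000 replicates): in about 18% of trials the 2-df test is significant and neither sham contrast is, even unadjusted.

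**Aim 1, price of naming and adjusting the contrasts.** One arm shifted by 0.4 SD: 0.4/0.1291 = 3.098.

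| Rule | Power for the sham contrast |
|---|---|
| Unadjusted | 87% |
| Pairwise only after a significant 2-df test | 84% |
| Holm over three contrasts | 79% |

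**Aim 2, two readings.** Error df 348. Section A's wording points to each CBT against Education-Only *within* active tDCS: SE = sqrt(2/30) = 0.258. Section B's wording on enhancement points to the difference between that contrast and the same contrast under sham: SE = sqrt(4/30) = 0.365.

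| Contrast | 0.6 SD | 0.8 SD |
|---|---|---|
| CBT minus Education-Only within one active arm, unadjusted | 64% | 87% |
| same, at 0.05/3 | 47% | 76% |
| Difference from the same contrast under sham, unadjusted | 37% | 59% |
| same, at 0.05/3 | 22% | 42% |
| same, at 0.05/3 and only if the 6-df test is significant | 17% | 36% |

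The last row is by simulation (200,000 replicates), with one cell shifted. The choice of reading, and of whether the 6-df test is a gate, changes the power several-fold. Neither choice is stated.

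**The case against.** *The factorial model is conventional and already contains the interaction; follow-up tests are routine.* The first part stands: the combination has an omnibus test, and Analysis does name tolerance change as the outcome for the stimulation test. But with three tDCS and four CBT levels, the choice of follow-ups and adjustment is not routine, and none is given.

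*The +0.2/-0.2 example detects a real 0.4 SD difference that Aim 1 also asks about, and the low sham power comes from the small assumed effect.* This stands as far as it goes. Naming the contrasts does not raise their power: in that scenario each sham contrast is found in about 33% of trials after a significant 2-df test, or 25% with Holm. The example shows only that a significant omnibus result and a difference from sham are different findings.

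*Section H calls this a pilot.* That lowers the stakes somewhat. It does not supply the missing comparison with sham.

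Three stronger readings are tempting, and the documents do not support them.
- A reader might infer that the MANCOVA must dilute an effect on tolerance. This depends on correlations the documents do not give, and on the QST values being a wider battery. For a 0.8 SD shift in one cell, the univariate interaction test has 61% power. With 5, 8 and 13 measures the MANCOVA has about 29%, 23% and 17% at zero correlation, but about 80%, 72% and 60% at a correlation of 0.7. The loss can reverse.
- A reader might fault the 6-df test because it is equally likely to be significant for a harmful combination. That is true of any two-sided test; the estimates give the direction.
- A reader might conclude that the active arms should never be pooled. That depends on whether one polarity works or both.

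**Conclusion.** The point holds as a mismatch between aims and analysis: the section A questions are specific comparisons on heat tolerance, and the analysis section states none of them. A significant stimulation effect could be reported with no evidence against sham. Under the stated assumptions the omnibus test and a single sham contrast are significant in 79% and 34% of trials in one plausible pattern, and the omnibus test is significant in 90% with no anodal benefit in another. These percentages illustrate scale and depend on the assumed effects, equal allocation and full follow-up. The textual gap does not depend on them. The design can answer Aim 1. For Aim 2 the plan must first say which question it means. It should be corrected, but it does not invalidate the trial.

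**What to change.** In Section D, Analysis:
1. Make pre-to-post heat tolerance the single primary outcome, analysed univariately with the planned covariates. List the QST values and make those other than tolerance secondary.
2. Aim 1: prespecify anodal-sham, cathodal-sham and anodal-cathodal with familywise control. Testing the pairs only after a significant 2-df test is enough with three arms; Holm is an alternative.
3. Aim 2: keep the tDCS x CBT interaction on tolerance as the overall test. State which follow-ups answer the aim: each CBT against Education-Only within active tDCS, the difference of that contrast from sham, or both. Give the polarities covered, the adjustment, and whether the interaction test is a gate.

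Under Study Design and Procedures, confirm that the post-stimulation trials, labelled quantitative sensory testing, are the same heat tolerance trials as the five at baseline.

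**Cost.** If they are the same trials, this is a change of wording with no new data. If not, procedures must also be reconciled. For Aim 1 the power loss is small (87% to 84% or 79% at 0.4 SD). For Aim 2, difference-in-difference contrasts have low power with 30 per cell (37% at 0.6 SD and 59% at 0.8 SD before adjustment), and the plan should say so. A univariate primary analysis is also less sensitive to an effect spread over several QST measures.
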